11.1.2 Medications administered during the bronchoscopy

The procedure anesthetic will be administered according to standard local protocols used for bronchoscopy. Assessment of collateral ventilation using the Chartis System will be performed under conscious sedation with unassisted breathing. The study procedure (EBV placement) may be performed under conscious sedation with unassisted breathing or under general anesthesia with the patient on a ventilator.

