11.4 Assignment to Study Treatment Arm

If the study participant is randomly assigned to the EBV treatment arm, (s)he should immediately undergo the study procedure (see Section 11.5). However, in any case in which there may be insufficient time to complete the study procedure because the time to safely administer the anesthesia is running out, the study procedure may be deferred. The study participant will be followed up as described in Section 8.10 and Appendix 12.

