12.0 SECONDARY VALVE PROCEDURES

Any study participant who receives EBV treatment may undergo valve removal, replacement, or adjustment while participating in the study. In the case of a secondary valve procedure(s), the follow-up schedule will be calculated from the date of the initial treatment. These procedures and the conditions in which they may be considered are described below.

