12.3 Valve Adjustment

It is anticipated that there may be a few cases in which a valve may not have been initially placed to occlude the treated lobe. In any case where clinical evidence exists that a valve was not placed to block the airway leading into the target lobe, adjustment of the valve may be considered by the investigator. Valve adjustment will be considered to be part of the study procedure since clinical effect with the Pulmonx EBV is thought to be associated with placing valves to achieve lobar occlusion.

Valve adjustment may be performed only once for a study participant and should be performed within 75 days of the study procedure. In any case in which it is necessary to re-schedule a valve adjustment due to a study participant's illness (e.g. COPD exacerbation), the valve adjustment may be conducted up to 90 days post-procedure.

The investigator may consider valve adjustment if both of the following are observed:

- 1) The 45-day HRCT scan, as read by the core radiology reading laboratory and measured using FDA cleared software designed to evaluate HRCT changes, shows less than 50% volumetric reduction in the EBV-treated lobe.
- 2) The 45-day HRCT scan, as read by the core radiology reading laboratory, demonstrates signs indicative of incomplete occlusion, including no valve in a segmental airway, anatomic variation resulting in the valve not occluding accessory branches, leakage around the valve, and incorrect placement.

The post-procedure flow and follow-up testing schedule for study participants having valve adjustment is shown in **Appendix 1** and **Appendix 12**. The bronchoscopy procedure for the valve adjustment will be conducted as described in Section 11.

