15.0 SAFETY ELEMENTS

15.1 Adverse Events

Previous studies of emphysema patients who were followed longitudinally and treated using medical management [10,16,17], diagnostic or interventional bronchoscopy [448,49], or endobronchial valves [16,17] indicate that a moderate risk of adverse events may be anticipated during this study. Adverse events will be graded by defining their severity and relatedness to the study device.

It is anticipated that the rates for adverse events will be higher for the study treatment arm than control arm during the treatment period ('short', or day of the study procedure to 45 days) but that the rates for these occurrences will be similar for both study arms during the post-treatment period ('long', or 46 days to 1 year).

Adverse events that may be observed include:

- ❖ Cardiovascular events such as:
 - New onset cardiac arrhythmia
 - New diagnosis of congestive heart failure, which may be indicated by ≥ 1 -point increase in NYHA functional classification score
 - Acute myocardial infarct requiring medical care
 - New diagnosis transient ischemia attack (TIA) or stroke
 - New diagnosis deep vein thrombosis
 - Pulmonary embolism, which may be indicated by direct clinical evidence or V/Q evidence of segmental or larger perfusion defects

- ❖ COPD and Emphysema events such as:
 - COPD exacerbation requiring treatment with antibiotics and/or oral steroids
 - AECOPD requiring emergency room visit or hospitalization
 - Respiratory failure requiring re-intubation at any time during follow-up and/or invasive mechanical ventilation >24 hours after the bronchoscopy procedure
 - Pneumonia requiring treatment with antibiotics, indicated by consolidation on X-ray or CT scan and clinical characteristics of active infection (fever, leukocytosis, hypotension)

- ❖ Pulmonary / Thoracic events such as:
 - Hemoptysis requiring new evaluation or intervention
 - Pneumothorax indicated by clinical symptoms and/or X-ray
 - Pneumothorax requiring intervention
 - Empyema requiring new evaluation or intervention
 - Non-cardiac chest pain driving the study participant to seek medical care
 - Pleural effusion noted radiologically
 - Lung mass / cancer noted radiologically
 - Fractured rib noted radiologically
 - Laryngospasm driving the study participant to seek medical care
 - Dysphonia driving the study participant to seek medical care
 - Hypoxemia requiring increased or new oxygen use

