inter-lobar fissures	percent complete	percentage of participants

V. Adjustment for Potential Confounders

The covariates shown in Table 6 may be potentially influential with respect to the effectiveness endpoints. If any of these covariates are found to be out of balance between the groups (at the two-sided 0.10 level), they will be included in a multivariate analysis, along with an indicator of treatment group, to evaluate their potential effect on the study conclusions. A multivariate logistic regression model will be used for primary and secondary endpoints.

Table 6. Covariates

	Baseline	Procedure
Gender	X	
Age	X	
Clinical Site	X	
6MWD	X	
Patient-reported health status measures (e.g. SGRQ)	X	
Body Mass Index	X	
BODE Index	X	
Medication Use	X	
Residual Volume (RV)	X	
RV % Predicted	X	
Total Lung Capacity (TLC)	X	
TLC % Predicted	X	
RV/TLC	X	
IC/TLC	X	
Vital Capacity	X	
Forced Vital Capacity (FVC)	X	
FVC % Predicted	X	
FEV ₁	X	
FEV ₁ % Predicted	X	
FEV ₁ / FVC	X	
Lobar Volume	Х	
Lobar Destruction Scores	Х	
Ipsilateral DS Heterogeneity	X	
Severity of emphysema (GOLD classification)	X	
Comorbidities	X	
Target Treatment Lobe		Х
Treatment Group		Х

VI. Secondary Valve Procedures

Secondary valve procedures will be evaluated by examining the proportion of patients who undergo valve removal, valve replacement, or valve adjustment, and describing the reasons they occurred. Data for these study participants will be contrasted to data for study participants who did not receive a secondary valve procedure.

VII. Safety Analyses

Evaluation of the short- and long-term adverse events profile during the treatment period, defined as the day of the study procedure until 45 days after the study procedure (short), and in the post-treatment period, defined as 46 days after the study procedure until the 1-year follow-up visit (long). For the Control arm, the date of study procedure will be considered the date of the bronchoscopy assessment. Safety analyses will be performed by examining the percentage of patients that experiences adverse events. The rates and 95% exact confidence intervals will be presented on an event and on a per-patient basis. The percentage of subjects reporting adverse events occurring in at least 3% of subjects in either treatment arm will be compared using a Fisher's Exact test.

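### SAP VII starts the EBV safety periods at valve placement but the control periods at the bronchoscopy, so events before a deferred placement fall in neither period and EBV participants never treated have no day 0

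*SAP*

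**What the plan says.** SAP VII defines two safety periods: "defined as the day of the study procedure until 45 days after the study procedure (short" and "defined as 46 days after the study procedure until the 1-year follow-up visit (long". It adds one anchoring rule: "For the Control arm, the date of study procedure will be considered the date of the bronchoscopy assessment". It has no rule for an EBV participant whose valves are placed on a later day, or never.

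In the EBV arm the protocol keeps the study procedure apart from the Chartis bronchoscopy. Section 11.1.2 says "The study procedure (EBV placement) may be performed under conscious sedation", after a separate sentence on the Chartis assessment, and section 11.5 dates the start of treatment from the introduction of the valve delivery catheter. Randomization takes place during the Chartis bronchoscopy (8.9.1, 11.2). If anaesthesia time runs short, "the study procedure may be deferred" (11.4; likewise 8.8); no maximum delay is stated. Adverse event collection begins at random assignment (21.1). The ITT population includes participants who never undergo their assigned treatment (20.1), and SAP III.D uses ITT, alongside As Treated, for safety.

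For later valve procedures, section 12.0 says "the follow-up schedule will be calculated from the date of the initial treatment". Section 12.3 says "Valve adjustment will be considered to be part of the study procedure". It requires a core-laboratory reading of the 45-day HRCT and allows the adjustment up to day 75, or day 90 if illness forces rescheduling. Section 15.1 expects more events in the EBV arm in the short period and that "the rates for these occurrences will be similar for both study arms during the post-treatment period".

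**The concern.** The 2017 SAP revision removed the restriction of the safety endpoint to the EBV arm, so that events are compared between arms in each period, and added Fisher's exact tests. Day 0 therefore decides which events enter a between-arm comparison, and it is not the same event in the two arms.

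Both arms undergo the same randomizing bronchoscopy. For a control, its aftermath opens the short period. For an EBV participant with deferred placement, the same aftermath comes before the short period and has no place in either table. Omitting those events can only lower the EBV short-period count. For an EBV participant who is never treated, the SAP gives no date from which to count, so two analysts could handle the same person differently.

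The secondary issue is the label on adjustment events. The protocol calls an adjustment part of the study procedure, yet the fixed clock places almost all of its acute aftermath in the long period, where the protocol expects the arms to look alike.

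**Working it through.** The plan gives no figure for deferrals, untreated EBV participants or adjustments, so there is nothing of its own to reproduce. The check is day arithmetic.

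**1. Day 0 by type of participant.** Let k be the number of days from the randomizing bronchoscopy to valve placement, with days counted from the bronchoscopy.

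| Participant | Day 0 under SAP VII | Short period | In neither period |
|---|---|---|---|
| Control | bronchoscopy | days 0 to 45 | none |
| EBV, placed in the same session (k = 0) | same day | days 0 to 45 | none |
| EBV, placement deferred by k days | placement | days k to k + 45 | days 0 to k − 1 |
| EBV, never treated | none | undefined | undefined |

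For illustration, take k = 7 (an assumption). The EBV short period covers days 7 to 52 after the bronchoscopy, and days 0 to 6 belong to no period. A control's days 0 to 6 are all in the short period.

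Starting at the bronchoscopy and ending 45 days after placement gives k + 46 days, against 46 for a control; at k = 7 that is 53 against 46. This window contains the literal one, so the literal EBV short-period count can be equal or lower, never higher. For k = 0 nothing changes.

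**2. Adjustment.** For an adjustment on day d after initial placement, the 46 days from d to d + 45 overlap days 0 to 45 by max(0, 46 − d) days:

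- d = 35: 11 of 46
- d = 40: 6 of 46
- d = 45: 1 of 46
- d = 46 or later, including days 75 and 90: 0 of 46

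The core laboratory has up to 5 working days to report (HRCT overview, Appendix 6), about 7 calendar days. A scan on day 45 with full turnaround gives d of about 52 and no overlap. The 45-day visit window is ±5 days in section 14.9 and ±10 days in the table of section 8.10.2, which must be reconciled. With full turnaround the earliest scans give d = 40 + 7 = 47 (no overlap) or d = 35 + 7 = 42 (4 of 46). Only an early scan leaves any overlap.

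**3. Size of the adjustment point.** EBV participants: 190 × 2/3 = 126.7, about 127 (split assumed from the 2:1 ratio). The adjustment rate is not given; section 12.3 anticipates only a few misplaced valves. The pneumothorax figure of 15% to 20% in section 15.3.1 is per participant in a VENT subgroup; applying it again after an adjustment is an assumption.

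| Assumed share adjusted | Participants | Pneumothoraces at 15% / 20% |
|---|---|---|
| 5% | 6.4 | 0.95 / 1.3 |
| 10% | 12.7 | 1.9 / 2.5 |
| 20% | 25.4 | 3.8 / 5.1 |

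The first row fits the protocol's expectation best: about one event.

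**The case against.** On deferral, the other side can say that it is a contingency for insufficient anaesthesia time and so probably rare, that the events are still collected from randomization, and that SAP VIII already runs mortality from randomization. All of this stands and limits the size. It does not fill the gap: the two periods are the safety endpoint, and SAP VII names no other place for these events.

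On adjustment, the opposing case is stronger:

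- A fixed clock gives both arms equal windows, which a per-patient comparison needs, and controls have no valves to adjust in year 1. Reopening the short period for an adjustment after day 45 would give that EBV participant 46 + 46 = 92 short-period days against 46, conditional on something that happened after randomization.
- The events are not lost. They count in the long period, can be classed as procedure-related (SAP VII), and belong to participants contrasted separately (SAP III.E and VI).
- Counting them as long-term works against EBV in that period, not for it.
- Section 12.0 speaks of the follow-up schedule, and the SAP does not literally say initial placement only. That reading comes from 12.0 together with 12.3, which dates the adjustment itself in days from the study procedure.

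These points stand, so the adjustment issue supports an extra display and no change to the main comparison.

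**Conclusion.** The deferral point holds. Followed literally, SAP VII leaves the pre-placement events of deferred EBV participants outside both periods while counting the same days for controls, and it gives EBV participants never treated no day 0 in the ITT safety analysis. Any bias in the short-period comparison favours EBV. Its size cannot be computed, because neither the number affected nor the length of a deferral is given; it is probably small.

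The adjustment point holds as a matter of labelling: acute events after an adjustment are almost always tabulated as long-term. At an assumed 5% adjusted, about one pneumothorax is involved.

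A reader might infer more, but the documents do not support it:

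- That the short-term rate materially understates harm. No deferral or adjustment rate is given, and few adjustments are expected.
- That most valve removals also fall in the long period. Section 15.4 cites 31 VENT removals (14.5%) without timing, and sections 12.1 and 12.2 do not supply it.
- That relabelled events would trigger the Fisher comparison. The 3% rule needs 4 of 127 (0.03 × 127 = 3.8), which these assumptions reach on average only near 20% adjusted, or about 25 participants. Nor does SAP VII say that the rule applies period by period.

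**What to change.** In SAP VII, state one day 0 for both arms:

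1. The treatment period starts at the randomizing bronchoscopy in both arms.
2. If EBV placement is deferred, pre-placement events count in the short period, which then runs to 45 days after placement; the long period follows.
3. EBV participants never treated use the bronchoscopy date, as controls do.
4. Report how many EBV participants were deferred, the length of each deferral, and how many were never treated.

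For valve adjustment, keep the fixed clock from initial treatment as the main between-arm comparison and say so explicitly, so that sections 12.0 and 12.3 and SAP VII can be read together. Add one supplementary EBV-arm table of events within 45 days of any adjustment or other secondary valve bronchoscopy.

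The cost is a few sentences and one table. Sites already have to keep the date of each study treatment (protocol 24.5.3). The downside is k extra days of short-period exposure for each deferred EBV participant; reporting the deferral lengths makes that visible. No clinical rule changes.

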8.10.2 Visit Windows

The study follow-up visits required by the study protocol are shown in the Table below. The study follow-up visits should be scheduled within the ranges

(windows) specified in the Table. These windows have been established to allow for maximum data collection in a study population known to have a high risk of missing clinic visits due to confounding clinical circumstances. It is recommended that all efforts be made to schedule follow-up visits as early as possible within the visit window in case the visit may need to be rescheduled. Utilization of these visit windows will aid in avoiding imputation of data during statistical analysis.

Study-related testing should not be conducted if the study participant is having an active COPD exacerbation at the time of a study follow-up visit. If a study participant has a COPD exacerbation, the study visit should be cancelled and rescheduled to be conducted at 14 days, or as early as possible after 14 days, following the initiation of treatment for the exacerbation. The clinical study site will document in the study participant's medical record all incidents in which a scheduled study visit is cancelled and rescheduled due to occurrence of a COPD exacerbation.

When the study participant informs the site of the COPD exacerbation, the investigator may request the study participant to come in for evaluation. This evaluation may include a physical examination and review of medications and will be classified as an interim visit.

If the rescheduled study follow-up visit falls outside of the study follow-up visit window, it will be recorded as an out of window protocol deviation. If the study participant fails to make the rescheduled study follow-up visit it will be captured as a missed visit and protocol deviation.

Table. Study Follow-Visits and Windows for Scheduling the Visits

	Visit	Range
1	24-Hour [‡]	+/- 8 hours
2	Daily phone call for 10 days following discharge [‡]	by 11:59 pm local time
3	7 days after discharge [‡] (phone call not required on this day)	+ 1 business day
4	30-day [‡]	+/-5 days
5	45-day	+/- 10 days
6	3-Month	+/- 14 days
7	6-Month	+/- 21 days
8	9-Month	+/- 21 days
9	1-Year	+/- 45 days
10-13	2, 3, 4, 5 Years [‡]	+/- 60 days
[‡] EBV-treated study participants only; *Procedure day = Day 0		

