14.9 Day 45 Visit (+/- 5 days)

- Vital Signs/Physical Exam
- Medication Use
- Daily Diary Collection
- Spirometry
- Body Plethysmography
- DLco
- Collect mMRC Survey
- 6-Minute Walk Distance
- Adverse Event Assessment
- Study Treatment Arm
 - Chest X-ray
 - HRCT Scan (may be completed in a separate visit)
 - Forward CT scan to core lab

14.10 3 Month Visit (+/- 14 days)

- Vital Signs/Physical Exam

- Medication Use
- Daily Diary Collection
- Collect SGRQ Survey
- Collect Health Care Utilization Survey
- Collect TDI Survey
- Collect CAT Survey
- Study Treatment Arm
 - Only EBV treated participants who undergo valve adjustment -- may be completed in a separate visit
 - HRCT, forward CT scan to core lab
 - Chest X-ray
 - Body Plethysmography

14.11 6 Month Visit (+/- 21 days)

- Vital Signs/Physical Exam
- Medication Use
- Daily Diary Collection
- Spirometry
- Collect SGRQ Survey
- Collect Health Care Utilization Survey
- Collect mMRC Survey
- Collect TDI Survey
- Collect CAT Survey
- 6-Minute Walk Distance
- Adverse Event Assessment

14.12 9 Month Visit (+/- 21 days)

- Medication Use
- Daily Diary Collection
- Collect TDI Survey
- Collect CAT Survey
- Collect Health Care Utilization Survey

14.13 1 Year Visit (+/- 45 days)

- Vital Signs/Physical Exam
- Medication Use
- Daily Diary Collection
- Spirometry
- Collect SGRQ Survey
- Collect Health Care Utilization Survey
- Collect SF-36 Survey
- Collect EQ-5D Survey
- Body Plethysmography
- DL_{co}

- Collect TDI Survey
- Collect CAT Survey
- Collect mMRC Survey
- 6-Minute Walk Distance

The following may be completed in a separate visit or in order as scheduling permits after all other testing

- ECG
- Blood Work (ABGs, CBCs, plasma cotinine, serum fibrinogen)
- Adverse Event Assessment
- Study Treatment Arm
 - HRCT Scan for EBV treated participants
 - Forward CT scan to core lab
- Control Arm
 - After completing the 1-year visit testing, assess suitability for crossing over to study treatment.
 - The study investigator must document the participant's suitability for crossing over to study treatment; to qualify for crossover, a control arm participant must have been followed up successfully through 1 year and demonstrate lack of a clinically important response
 - The crossover procedure must be scheduled to occur within the next 60 days following the 1-year visit

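### The SAP compares long-period adverse events as crude percentages, with no allowance for time at risk and no stated denominator, so an arm difference in exposure could not be told from one in risk

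*SAP*

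**What the plan says.** SAP VII (Safety Analyses) splits follow-up in two. The short period runs from the procedure to Day 45. The long period is "defined as 46 days after the study procedure until the 1-year follow-up visit (long"). Its end is therefore a personal visit date. Protocol 14.13 sets that visit as "1 Year Visit (+/- 45 days"), and the table in Protocol 8.10.2 gives the same window. Section 8.10.2 also recommends that "all efforts be made to schedule follow-up visits as early as possible within the visit window".

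The window is not a hard limit. A rescheduled visit may fall outside it, and then "it will be recorded as an out of window protocol deviation". If a participant has an active COPD exacerbation, "the study visit should be cancelled and rescheduled to be conducted at 14 days" after treatment starts, or as soon as possible after that.

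The measure is crude: "Safety analyses will be performed by examining the percentage of patients that experiences adverse events". The between-arm test is stated as follows: "The percentage of subjects reporting adverse events occurring in at least 3% of subjects in either treatment arm will be compared using a Fisher's Exact". The SAP change history gives comparison of the arms in both periods as the reason for rewording the safety endpoint.

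SAP VII also promises exact-interval rates per event and per patient, but defines no person-time denominator. Kaplan-Meier, log-rank and Cox methods are planned in SAP VIII for death only. The missing-data rules in SAP IX cover the primary and secondary effectiveness endpoints, not adverse events.

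**The concern.** A percentage of subjects estimates risk over a period only if everyone is observed for the same period, or if departures are handled. Here the period differs between completers and is cut short by death, withdrawal or a missed visit. The SAP does not say whether someone who left before Day 46 counts in the long-period denominator.

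An arm difference in follow-up could then appear as a difference in risk, or hide one. Protocol 15.1 expects more adverse events in the EBV arm up to Day 45 and similar rates in both arms afterwards. Shorter exposure in the EBV arm would push a crude comparison towards that expected similarity when EBV carries the higher risk.

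The exacerbation rule adds a further difficulty. COPD exacerbation is one of the events compared, and it can postpone the visit that closes the period, so the length of follow-up can depend on the outcome.

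**Working it through.** The documents give no expected long-term event rate and no power for the safety comparison, so there is no plan figure to reproduce.

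**Inputs from the documents**
- Long period: Day 46 to the 1-year visit (SAP VII). Window: 365 − 45 = Day 320 to 365 + 45 = Day 410 (Protocol 8.10.2 and 14.13).
- 190 enrolled (SAP, Study Design), randomized 2:1.
- 20% allowance for loss and incomplete data, not split by arm (Protocol 20.3.1).

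**Assumptions**
- A 127:63 split, constant hazards, the event risks R used below, and all exit patterns by arm.

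**1. Length of the period, counting both end days.** Visit on Day 320: 320 − 46 + 1 = 275 days. Day 365: 320 days. Day 410: 365 days. Ratio 365/275 = 1.33.

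**2. Level of the crude percentage.** Daily hazard λ = −ln(1 − R)/320 and P(d) = 1 − exp(−λd), where R is the risk over 320 days.

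| R | P(275) | P(365) |
|---|---|---|
| 10% | 8.7% | 11.3% |
| 20% | 17.4% | 22.5% |
| 30% | 26.4% | 33.4% |
| 50% | 44.9% | 54.6% |

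These are bounds on level, not expected arm differences.

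**3. Fisher's test with equal hazards.** Exact rejection probability at two-sided 0.05, summed over both binomials:

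| Scenario | R = 10% | 20% | 30% | 50% |
|---|---|---|---|---|
| Same timing, no exits | 3.4% | 3.8% | 4.1% | 4.4% |
| 20% exits in both arms | 3.4% | 3.8% | 4.0% | 4.4% |
| Mean period 327 v 313 days (14-day gap) | 3.4% | 3.9% | 4.2% | 4.8% |
| All EBV on Day 410, all control on Day 320 | 5.6% | 9.7% | 13.9% | 22.4% |

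**4. EBV exits before Day 46, if kept in the denominator.** The EBV percentage becomes R(1 − d), where d is the fraction who exit; 3% to 8% is an assumed range.
- R = 20%: 19.4% (d = 3%) and 18.4% (d = 8%). Rejection 4.0% and 4.7%.
- R = 50%: 48.5% and 46.0%. Rejection 4.8% and 7.1%.

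**5. Masking of a true excess.** Control risk 20%, hazard ratio 1.5, so EBV risk = 1 − 0.8^1.5 = 28.4%. Exits are assumed uniform over the 320 days and kept in the denominator. Someone who exits has an average observed risk of 1 − (1 − e^(−λT))/(λT) with T = 320: 15.0% in EBV and 10.4% in control.
- EBV with 20% exits: 0.80 × 28.4% + 0.20 × 15.0% = 25.8%.
- Control with 5% exits: 0.95 × 20.0% + 0.05 × 10.4% = 19.5%.
- Power falls from about 20% (28.4% v 20.0%) to 12.5% (25.8% v 19.5%).

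**6. With time at risk counted.** At equal hazards the rate ratio is 1.00 whatever the visit day or exit time. For R = 20% the rate is 0.000697 × 365 = 0.255 per person-year in each arm. Cumulative incidence at a common day is also equal if censoring is non-informative.

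**The case against.** The strongest reply is that nothing in the documents shows exposure to differ by arm. The advice to book early applies to everyone and tends to align follow-up. With the same timing and exits, the test keeps its size, and a two-week gap does not raise it above 5%. Even the 4-point shift from 8% early exits is only about half the standard error of the difference, √(0.25 × (1/127 + 1/63)) = 7.7 points. Study success rests on FEV₁ alone, and the safety endpoint carries no hypothesis or margin. Death already has time-to-event methods. SAP I promises that denominators for dichotomous variables will be reported and defined. All of this stands, and it limits the weight of the point.

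A reader might go further in three ways, none of which the documents support:
- **Reading 44.9% against 54.6% as an arm difference.** That needs every participant in one arm to attend on Day 320 and every participant in the other on Day 410. Nothing suggests this.
- **Supposing that controls come early because crossover follows the 1-year visit.** No passage says so. Crossover also depends on continued eligibility, lack of a clinically important response (Protocol 7.5) and the interim review (Protocol 7.6).
- **Taking it that the plan counts early EBV exits as event-free.** SAP VII does not state the long-period denominator, and Protocol 15.1 forecasts more adverse events, not more deaths or withdrawals.

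The reply does not remove the gap. A promise to define the denominator later is not a definition, and no planned analysis of non-fatal events would reveal unequal exposure or correct for it.

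**Conclusion.** The point holds as a conditional weakness that is cheap to repair. The long-period comparison ignores time at risk and leaves its denominator unspecified. If timing and exits match between arms, only the level of the percentages moves. If they do not, a difference in exposure cannot be separated from a difference in risk.

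Unequal exit is the more credible route; modest differences in visit timing matter little. Inflation is small except for common events with clearly unequal exits. Loss of power to see a true excess is the larger effect in the cases examined. It would be too strong to call the long-term comparison uninterpretable. The sizes rest on constant hazards, a 127:63 split and exit rates that are assumptions throughout. The effect of exacerbation-driven postponement was not quantified.

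**What to change.** In SAP VII:
- Keep the crude percentages and Fisher p-values as the descriptive adverse event tables.
- State the long-period denominator: participants under follow-up on Day 46, with the full ITT and As-Treated denominators also shown.
- For the main and serious events, add cumulative incidence from Day 46 to Day 365. Treat death as a competing event, and censor at exit, crossover or last adverse event assessment. Give the arm difference with a 95% CI.
- Repeat this to Day 320 as a sensitivity analysis, since that day needs no follow-up beyond any in-window 1-year visit.
- Report cumulative incidence from the procedure date in all randomized participants as well. The Day 46 restriction conditions on retention after randomization, and censoring at exit may be informative.

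Onset dates are already recorded (Protocol 21.1), and SAP VIII already plans survival methods for death. No new data or visits are needed. The cost is some extra programming and an explicit statement of the censoring and competing-event assumptions.
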